-  Patients will receive one dose of tremelimumab 75 mg (if on Arm 1), MEDI4736 750 mg (if on Arm 2) or the combination of both (if on Arm 3) approximately 2 weeks (14 days +/- 7 days) before surgery.
-  Tumor from prior surgeries will be requested on all patients. Tissue will be analyzed in the [name] Laboratory. Please refer to Section 9.3 and laboratory manual for details.
-  Blood samples will be collected for various research tests at 1 st pre-operative treatment, day of surgery, C1D1 and at each adjuvant treatment imaging visits (i.e. every 2 cycles or 8 weeks):
  - a) 10ml blood in one 10ml Sodium heparin tube: To be collected and processed by the [name] lab for peripheral blood lymphocytes (PBLs).
  - b)8m (2x4ml) blood in two 5ml EDTA (purple top) tubes: To be collected and processed by the [name] lab for gene expression profile using mononuclear cells.
  - c) 10ml blood in one 10ml red top tube: To be collected and processed by the [name] lab for analysis of tryptophan catabolites and cytokines.

Please refer to section 9.0 and laboratory manual for more details

 Chemistries should include electrolytes, calcium, , albumin, alkaline phosphatase, bilirubin (total), SGPT(ALT), SGOT(AST), serum creatinine, and BUN.

 TSH, T4, T3

 Required at baseline only but may be repeated as clinically indicated thereafter.

 Includes hepatitis A antibody, hepatitis B (HBsAg reactive), and Hepatitis C (HCV RNA [qualitative] detection).

 Please refer to Section 9.1 and the laboratory manual for details.

Time Period	Adjuvant Treatment 		Off Treatment			
Assessment/Activity	Cycle 1 Day 1  (+/- 2d)	Cycle 2 Day 1 (+/- 2d)	Cycle 3+ Day 1 (+/- 2d)	Treatment Discontinuation	90 Days Post Last Dose (+/- 7d)	Follow-up 
Concomitant medications	X	X	X			
Toxicity assessment	Х	Х	X	X	X	
Neurological exam and KPS 	Х	X	X	Х	Х	
Vital signs & weight 	X	X	X			
CBC with diff 	X		X	X	Х	
Comprehensive Chemistry Panel	X	X	X	X	Х	
Thyroid Function Tests 	X		X	X	Х	
ECG 	X			X		
Tumor Imaging (MRI/CT)	X 		X 	X 		
Tremelimumab monotherapy 	Х	X	X			
MEDI4736 monotherapy 	X	X	X			
Combination therapy 	X	X	X 			
Research tissue		X 	·			·

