#### **8.2.13** Accountability and dispensation Drug will be kept in the research pharmacy at Northwestern Memorial Hospital.

### 9.0 CORRELATIVES/SPECIAL STUDIES

#### 9.1 Tumor and peripheral lymphocyte changes

Samples will be collected and sent to the laboratory of: [name] [name] Lab [contact] Office [contact] [name] Tissue and blood samples from the operating room and from clinic will be collected by laboratory personnel and sent to the laboratory of [name] in [name] for processing.

**Fresh Tumor tissue**: removed at surgery will be used to extract tumor-infiltrating lymphocytes (TIL) for analysis. In addition, fresh frozen and formalin fixed paraffin embedded tissue will be banked for analysis. Extracted TILs will be used to evaluate the tumor infiltrative lymphocyte population by flow cytometry and paraffin embedded tissue will be used to evaluate TILs in situ by immunohistochemistry. If a patient has progression of disease and undergoes further surgery, they will have the option of allowing tissue to be analyzed for the above.

**Blood sample**: 10ml blood in one 10ml Sodium heparin tube. This will be collected at 1st preoperative treatment, day of surgery, C1D1, and at each adjuvant treatment imaging visits (i.e. every 2 cycles or 8 weeks).

Blood collected prior to treatment on 1st pre-operative treatment day will be used for baseline evaluation of activated peripheral lymphocytes. Patients will then have blood drawn on day of surgery, and on the day of each MRI scan (i.e. every 2 cycles or 8 weeks) with extraction and banking of peripheral blood leukocytes (PBL).

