PBLs obtained prior to drug administration will be studied by flow cytometry to identify relative populations of CD8 T cells (CD3+, CD8+, PD1+/-), CD4 T cells (CD3+, CD8+, PD1+/-), regulatory T cells (CD4+, CD25+, FoxP3+), and suppressive monocytes (CD45+, CD11b+, PD-L1+). Repeat assessment of PBL markers will be determined by flow cytometry of subsequent samples taken on the day of surgery, post operatively (C1D1) and then on MRI days. Additionally, TILs extracted from patient tissue will be evaluated for relative populations of activated CD8 T cells (CD3+, CD8+, IFN-g+, PD1+/-), activated CD4 T cells (CD3+, CD8+, IFN-g+, PD1+/-), regulatory T cells (CD4+, CD25+, FoxP3+), and suppressive monocytes (CD45+, CD11b+, CD163+, PD-L1+). CTLA-4 expression on effector and regulatory T cells can also be measured by flow cytometry. Double-labeled tissue immunofluorescence can also be performed on FFPE sections to obtain immune effector cell counts, reported as # cells / 10 hpf. Optimized labeling schemes include: CD8/IFN-g, CD4/IFN-g, CD8/PD-1, CD4/PD-1, CD68/PD-L1, GFAP/PD-L1 (to identify PD-L1+ tumor cells).

We will use our stimulation protocol for IFN-g from PBL to look for increased peripheral T cell reactivity before and after drug treatment

Banked PBLs, TILs and FFPE tissue from prior patients treated without the study drug will serve as comparative controls.

*NOTE:* Any leftover tissue from the study patients will be banked for future use. This should be clearly stated in the consent form.

Please refer to laboratory manual for further details on collection, labeling, shipping, processing and storage.

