#### 10.3 Sample Size, Accrual and Data Analyses Plans

There will be three groups of patients, one group on each agent alone and one group treated with the combination agent. There will be 10 patients per group for a total of 30 patients. These 30 patients must be evaluable for the primary endpoint, meaning that they must have undergone surgery and their blood and tissue samples are available at both the pre- and post-surgery times. In order to attain 10 evaluable patients in each arm, a total of 45 patients will be accrued to the study. Sample sizes of 10 per group allow for the estimation of the proportion of responders in evaluable patients to be within 31% of its true value with 95% confidence. Mean change will be compared between arms. Using standard deviations of change, a sample size of 10 per group will allow the detection of differences of 1.25 standard deviations between groups with 80% power assuming a two-tailed test and a Type I error rate of 5%.

Immunologic measures will be summarized over the three or more time points (pre-treatment, following first treatment/pre-surgery, post-surgery) and changes in these measures will be assessed using repeated measures analysis of variance or Cochran's Q, followed by the paired t-test or the signed rank test for pairwise comparisons using Bonferroni corrections. Safety of the agents alone or in combination will be assessed by summarizing the frequency of adverse events by type, timing, grade and attribution. Response criteria will be based on RANO (including upcoming Immunologic RANO criteria) but since all patients will be post-surgery, the degree, if any, of

residual disease will vary. A patient is evaluable for efficacy if they have undergone at least one follow-up MRI after adjuvant therapy. Immunologic changes will be correlated with MRIs in a descriptive fashion. The secondary endpoint of progression-free survival as well as overall survival will be analyzed using Kaplan-Meier curves. Immunologic changes of T-cells and PDL1 levels will be correlated to survival outcomes using Cox regression analysis. MRI changes will be summarized using means or proportions and statistically analyzed using the signed rank test.

**Performance Status:** Patients will be graded according to Karnofsky Performance Status (KPS)(see appendix C).

**Evaluation of toxicity.** All patients will be evaluable for toxicity from the time of their first treatment as per NCI CTCAE version 4.03

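### Repeated measures ANOVA or Cochran's Q over an open-ended set of time points can shrink the omnibus T-cell test to patients still on treatment, and the evaluability rule sets aside usable early blood

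*Combined protocol and SAP*

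**What the plan says.** The primary objective (Sections 2.1 and 6.1) is T-cell change from baseline, compared between three arms. For the analysis, Section 10.3 and the Study Summary say that the measures are "summarized over the three or more time points (pre-treatment, following first treatment/pre-surgery, post-surgery"), and that "changes in these measures will be assessed using repeated measures analysis of variance" or Cochran's Q. These omnibus tests are "followed by the paired t-test or the signed rank test for pairwise comparisons using Bonferroni corrections". Mean change is also compared between arms. Three points are named; the wording allows more and does not say which.

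More points exist. Section 5.1 schedules research blood at the first pre-operative dose, then "day of surgery, C1D1 and at each adjuvant treatment imaging visits (i.e. every 2 cycles or 8 weeks"). Section 9.1 runs the same flow cytometry on "subsequent samples taken on the day of surgery, post operatively (C1D1) and then on MRI days". In the Section 5.2 table, the off-treatment columns carry no research blood.

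Section 6.1 counts a patient as evaluable for the primary endpoint only with blood before treatment, before surgery and before the first post-surgical dose (Cycle 1 Day 1, C1D1). Section 10.3 gives no rule for missing samples.

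**The concern.** Conventional repeated measures ANOVA and Cochran's Q both need a complete row for each patient. Every time point added to the test removes the patients who lack it. The 8-weekly samples measure the primary variable and are the obvious candidates for the extra points, yet they are scheduled only while adjuvant treatment continues. Treatment ends mainly for progression or toxicity, so the patients removed would not be a random subset. As worded, the plan lets the number of time points, and with it the analysed population, be settled after the data are seen.

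A second loss does not come from the ANOVA. A dosed patient who has pre-treatment and day-of-surgery blood but never reaches C1D1 informs the early contrast directly. Section 6.1 excludes that patient from the primary endpoint whatever test is used.

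**Working it through.** **1. The plan's own figure.** Inputs from Section 10.3: 10 per group, a difference of 1.25 SD of change, two-sided 5%. Normal approximation: 1.25 × √(10/2) = 2.795, and power = Φ(2.795 − 1.960) = 79.8%, which reproduces the stated 80%. (The noncentral t gives 75.3%.) The calculation presumes 10 patients per arm with both samples of the change being compared.

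**2. Three named points.** Section 6.1 requires all three blood samples, so 10 of 10 evaluable patients per arm have complete rows. The omnibus test loses nobody from the evaluable set.

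**3. Adding 8-weekly points.** The documents give no time-on-treatment distribution. Assume exponential time on treatment after C1D1 with median m months. Eight weeks = 56/30.4375 = 1.84 months, so complete rows per arm after k added samples = 10 × 0.5^(1.84k/m):

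| Assumed median m (months) | k = 1 | k = 2 | k = 3 |
|---|---|---|---|
| 2 | 5.3 | 2.8 | 1.5 |
| 3 | 6.5 | 4.3 | 2.8 |
| 4 | 7.3 | 5.3 | 3.8 |
| 6 | 8.1 | 6.5 | 5.3 |

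This is the loss to the omnibus test. The between-arm comparison and the paired tests need only the samples they compare. If, and only if, the complete-row set were carried into the between-arm comparison, its normal-approximation power for 1.25 SD would fall from 79.8% to 53-71% (k = 1) or 31-62% (k = 2) over the same medians.

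**4. Direction of the selection.** A simulation used 300 runs, arms pooled, 30 evaluable and 15 partial patients, correlation 0.5, two on-treatment samples, and a true pre-treatment to pre-surgery change of 0.60 SD. When patients with low pre-surgery values were made to leave sooner, the mean change among complete rows was 0.84, 0.79 and 0.71 for medians of 2, 3 and 6 months. The mixed model gave 0.60-0.62. The set restricted to the three named samples gave 0.60-0.61, so fixing the time points removes this distortion by itself.

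**5. Blood set aside by Section 6.1.** Up to 15 per arm are accrued for 10 evaluable (Sections 3.0 and 4.1). Assume, per arm, 10 patients with three samples, 3 with the first two and 2 with the first only, with compound symmetry, unit variance and correlation ρ.

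- Evaluable set only: SE of a change = √(2(1−ρ)/10).
- Plain paired analysis of all available pairs, baseline to surgery: √(2(1−ρ)/13). The ratio is √(10/13) = 0.877, a 12% cut.
- All samples, generalised least squares: the covariance matrix of the time means is (Σ XᵢᵀVᵢ⁻¹Xᵢ)⁻¹.

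| ρ | Baseline to surgery: SE, evaluable → all | Ratio | Baseline to C1D1: SE, evaluable → all | Ratio |
|---|---|---|---|---|
| 0.3 | 0.374 → 0.320 | 0.856 | 0.374 → 0.350 | 0.936 |
| 0.8 | 0.200 → 0.174 | 0.871 | 0.200 → 0.192 | 0.962 |

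The cut is 13-14% for baseline to surgery, about 12 points of it from widening the set. For baseline to C1D1 it is 4-6%, and this comes only from the model, because the five added patients have no C1D1 sample to pair. These figures treat the covariance as known; estimating it would reduce the gain a little.

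**The case against.** The strongest reply is that the plan names exactly three points, that Sections 2.1 and 6.1 frame the endpoint as before treatment against post-surgery, and that the evaluable set is complete at those points. On that reading nothing is lost from the ANOVA. This stands: use of the 8-weekly samples is left open, not planned.

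A reader might infer that early progressors vanish from all contrasts, and might compute paired power for a 1 SD change at 0.05/3 falling from 60% (n = 10) to 36% (7), 19% (5) or 6% (3). The documents do not support that. The pairwise tests and the comparison of mean change need only the samples compared, and nothing says that the ANOVA's complete-row set is carried into them.

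Nor does every progressor lose the later sample. On-treatment blood is drawn on imaging days, so progression found at the first scheduled scan coincides with a draw, and Section 6.4 allows treatment beyond confirmed progression. The clear losses are patients who stop before the added sample.

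A reader might also blame the ANOVA for discarding non-completers' blood, or blame uneven spacing for breaking sphericity. The first is the Section 6.1 rule; changing the model alone recovers nothing. Uneven spacing does not by itself violate sphericity, and the three named points are roughly evenly spaced.

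Finally, once the set is widened, available pairs do nearly as well as a mixed model for the early contrast (0.877 against 0.86-0.87). That also stands.

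**Conclusion.** The point holds in a limited form. The omnibus tests need complete rows over a set of time points that the plan leaves open, and the candidate extra samples stop when treatment stops. If one is added, the omnibus test would run on about 5 to 8 of 10 patients per arm for assumed medians of 2 to 6 months on treatment, selected in a way linked to outcome. With only the three named points there is no such loss. Harm to the paired and between-arm comparisons is conditional on a carry-forward that the plan neither states nor excludes.

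Separately, the evaluability rule costs some precision: 13-14% of the standard error for baseline to surgery and 4-6% for baseline to C1D1, on the assumed 10/3/2 pattern with correlation 0.3-0.8. Medians, pattern and correlations are assumptions. Forty-five is an accrual cap, and some of those accrued may never be dosed or reach surgery.

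**What to change.** In Section 10.3 and the Study Summary:

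- State that the primary analysis uses the three named time points.
- For continuous measures, use a linear mixed model with categorical time, arm and arm-by-time, an unstructured 3×3 covariance and small-sample degrees of freedom. Fit it to all available samples at those points from all dosed patients, and take the within-arm changes and between-arm differences from it.
- Report the 8-weekly samples separately as descriptive.
- Keep the repeated measures ANOVA and paired tests on the Section 6.1 evaluable set as a sensitivity analysis. Cochran's Q may stay for binary measures on the three points.

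The cost is wording and slightly more programming; no patients or samples are added. The model relies on data being missing at random. That is weaker than what a complete-row analysis needs, but it is not guaranteed when patients leave for progression or toxicity, so the sensitivity analysis should be reported beside it.

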# 5.2 Post-Surgery/Adjuvant Therapy

 Includes weight, BSA, and vital signs (temperature, blood pressure, pulse rate, and). Following the initial presurgery dose, for subsequent doses, the post dose vitals and 1-hour observation period will not be required unless a subject experiences an infusion-related reaction. Vital signs will be measured within an hour prior to start of study drug administration, at 30 minutes during the infusion (± 5 minutes), at the end of infusion (+ 5 minutes). If needed, vital signs will be done at 30 and 60 minutes (± 5 minutes each) post-infusion. If the infusion takes longer than 60 minutes, blood pressure and pulse measurements should follow the principles described here or more frequently if clinically indicated.

 Adjuvant treatment (cycle 1 day 1) will resume approximately 14 days (+/- 7 days) after surgery, once the surgical wound has healed.

 Will be done every other week while on adjuvant treatment.

 Will be done prior to each cycle (monthly) while on adjuvant treatment.

 If patients are unable to start treatment within 21 days of the post-surgical imaging, then repeat imaging with

enhanced MRI or CT scan should be performed prior to initiation of adjuvant therapy. During adjuvant treatment, contrast-enhanced MRI or CT scan will be done approximately every 2 cycles or 8 weeks (prior to each odd cycle). If there is no progression of disease, patients will continue on treatment for up to 24 months. If a patient has disease progression (as defined in section 6.4) or clinical decline and undergoes further surgery but is found to have no pathologic evidence of significant tumor, the patient may then re-start treatment.

-  Thyroid function tests will be done every 2 cycles (approximately every 2 months) during treatment. TSH will be done each time; free T3 and free T4 only if TSH is abnormal.
-  ECGs are required within 1 hour prior to starting study treatment and at least once after the infusion is completed (anywhere from 0-3 hours) on Cycle 1 Day 1, again after approximately 16 weeks on treatment, and at the end of treatment. ECGs may be repeated at any other time point if clinically indicated. ECGs recorded during the treatment phase will be single tracing. Twelve-lead ECGs will be obtained after the subject has been resting in a supine position for at least 5 minutes in each case.

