# 6.0 ENDPOINT ASSESSMENT

## 6.1 **Primary Endpoint**

To determine the T-cell changes (immunologic changes) that occur in recurrent GBM treated with Tremelimumab and MEDI4736 as single agents and in combination. The changes from baseline will be assessed in blood samples and tissue samples before treatment and post-surgery for all patients in the 3 arms. A comparison between the changes observed in the 3 arms will be made.

Only patients who have had pre-treatment blood sampling, have undergone surgery with pre-surgical blood sampling, and are able to continue to post-operative drug treatment with blood sampling prior to the first post-surgical dose will be evaluable for this endpoint.

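### Section 10.3 does not fix the Bonferroni family for the within-patient T-cell tests; read as all pairs at the three named time points, one of three tests is not a change from baseline

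*Combined protocol and SAP*

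**What the plan says.** The endpoint sections (2.1 and 6.1) define the within-patient question as change from baseline: "The changes from baseline will be assessed in blood samples and tissue samples before treatment and post-surgery for all patients in the 3 arms". They add a between-arm question: "A comparison between the changes observed in the 3 arms will be made". Section 6.1 ties evaluability to three blood samples, the last of them in patients who "are able to continue to post-operative drug treatment with blood sampling prior to the first post-surgical dose will be evaluable for this endpoint".

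Section 10.3, repeated in the Study Summary, sets the analysis. "Immunologic measures will be summarized over the three or more time points (pre-treatment, following first treatment/pre-surgery, post-surgery") and changes are assessed by repeated measures analysis of variance or Cochran's Q, "followed by the paired t-test or the signed rank test for pairwise comparisons using Bonferroni corrections". Neither place gives a list of pairs, a number of comparisons or an adjusted significance level.

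More than three samples will exist. Section 9.1 repeats the flow cytometry of peripheral lymphocytes on "subsequent samples taken on the day of surgery, post operatively (C1D1) and then on MRI days". Section 5.2 says that "contrast-enhanced MRI or CT scan will be done approximately every 2 cycles or 8 weeks (prior to each odd cycle"), with treatment for up to 24 months. Section 1.5.1 lists lymphocyte profiling, and tumor-infiltrating lymphocytes through the course of treatment, among the exploratory studies.

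**The concern.** Two features of the rule do not fit the endpoint.

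First, pairwise comparisons after an omnibus repeated-measures test ordinarily means all pairs. That family contains contrasts that 2.1 and 6.1 do not ask for, such as pre-surgery against post-surgery. Each one raises the Bonferroni divisor and so costs power on the contrasts that are asked for.

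Second, the divisor is not fixed, because the number of time points is left open. A baseline-to-surgery p-value of 0.012 passes with three time points (threshold 0.0167) and fails with four (0.0083). The trial is open-label, and nothing in the text prevents that number from being settled after data have been seen.

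At stake is whether a real T-cell change within an arm of 10 patients is called significant. The false-positive rate is not at stake in the first feature, since extra Bonferroni contrasts only make the test more conservative. The second feature matters for pre-specification.

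**Working it through.** **Inputs from the documents.** 10 evaluable patients per arm, two-sided 5%, and three named time points with more left open (10.3); change from baseline (2.1, 6.1); further T-cell samples on MRI days, every 8 weeks (5.2, 9.1).

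**Assumptions.** The documents give no within-patient effect size and do not say that the paired tests are run within each arm. I take tests within an arm, 10 complete patients, normal data and a true change of 1.0 SD of the change. For the simulations I also take correlation 0.5 between time points.

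**The plan's own figure.** For a between-arm difference of 1.25 SD with 10 per group, the normal approximation gives Φ(1.25·√(10/2) − 1.96) = Φ(2.795 − 1.960) = Φ(0.835) = 0.798, which reproduces the stated 80%. (The noncentral t gives 75.3%.) This concerns the comparison between arms and does not involve the time-point family. No power is stated for the within-patient tests.

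**Size of the family.** With T time points there are T(T−1)/2 pairs, of which T−1 are against baseline.

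- T = 3: 3 pairs, 1 not against baseline; 0.05/3 = 0.0167
- T = 4: 6 pairs, 3 not against baseline; 0.05/6 = 0.0083
- T = 5: 10 pairs, 6 not against baseline; 0.05/10 = 0.0050

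**Power per baseline contrast.** Paired t, 9 degrees of freedom, noncentrality 1.0·√10 = 3.162.

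| Family | Alpha per test | Critical t | Power | Change detectable with 80% power |
|---|---|---|---|---|
| One baseline contrast, unadjusted | 0.05 | 2.262 | 80% | 1.00 SD |
| Two baseline contrasts, Bonferroni | 0.025 | 2.685 | 68% | 1.14 SD |
| All pairs, T = 3 | 0.0167 | 2.933 | 60% | 1.22 SD |
| All pairs, T = 4 | 0.0083 | 3.364 | 47% | 1.37 SD |
| All pairs, T = 5 | 0.0050 | 3.690 | 38% | 1.48 SD |

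**Holm on the two baseline contrasts.** The smaller p-value is tested at 0.025 and, if it passes, the other at 0.05. Power per contrast therefore lies between the 68% and 80% rows, and where it falls depends on the true shift at the other post-dose time point. Simulated power for a contrast with a 1.0 SD shift:

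- Other shift 1.0 SD: about 75%
- Other shift 0.5 SD: about 69%
- No other shift: about 68%

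Family-wise error is about 0.05, however many later samples exist. Under the null, the chance of any baseline-contrast rejection is 0.046-0.049 with Holm, against 0.035 with all-pairs Bonferroni at three time points.

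**Holm on all three pairs.** Simulated power per baseline contrast is about 62-65%, against 60% for Bonferroni on the same three.

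**The case against.** The strongest reply is that this is mostly a wording gap. Section 10.3 never says every pair. Its parenthesis names exactly three time points, 6.1 requires exactly three blood samples, and 1.5.1 places lymphocyte profiling among the exploratory studies. On that reading the MRI-day samples are already outside the primary family and the cost is modest: 60% power against 68-75%. This stands, and it limits the size of the point. It does not remove it, because even at three time points the divisor is unstated and one pair lies outside the endpoint.

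A reader might go further and infer that the signed rank test could never reach significance. With 10 patients its smallest two-sided p is 2/2^10 = 0.00195, and eight time points give 0.05/28 = 0.00179. The documents do not support that as a description of the plan. It needs five MRI-day visits pooled into the primary family and tests run within arms of 10. Section 10.3 does not say that the tests are run by arm. If time were tested over all 30 patients, power for a 1.0 SD change at 0.0167 would be 99.7%.

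Two further replies have weight. Read literally, 6.1 could mean a single contrast, before treatment against post-surgery, so choosing two is a judgement. I keep both because each is a change from baseline and 6.1 requires both post-dose samples. Pre- against post-surgery is also a sensible question, since it helps separate the effect of the operation from that of the first dose. Dropping its formal test is a real, if small, loss.

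**Conclusion.** The point holds in a limited form. The family of within-patient contrasts is not fixed, and on the ordinary all-pairs reading at the three named time points a contrast outside the endpoint takes one of three Bonferroni shares. Within an arm of 10, for a true change of 1.0 SD, closing the family at the two baseline contrasts raises power per contrast from about 60% to 68% with Bonferroni. With Holm it is about 68-75%, a gain of roughly 8 to 15 percentage points at the same nominal family-wise error.

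The figures of 47% and 38% apply only if one or two MRI-day samples enter the family. The text permits that but does not prescribe it. All these figures rest on within-arm testing, normal data and complete samples; the Holm range also rests on the assumed correlation of 0.5.

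It would be wrong to read this as a fault in the sample size. The primary endpoint also includes the between-arm comparison, and the stated 80% power at 1.25 SD concerns that comparison and does not change. The point is also separate from multiplicity across T-cell measures or arms, which this change would not address. It is worth correcting before the within-patient analysis is run.

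**What to change.** In 10.3 and the Study Summary, delete the words *or more* for the primary analysis and replace the pairwise Bonferroni clause with wording such as:

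*For each immunologic measure, two baseline contrasts (pre-treatment to day of surgery; pre-treatment to C1D1 before dosing) are tested at two-sided 5% with Holm's procedure. The pre- versus post-surgery contrast and all contrasts with MRI-day samples are exploratory and are reported as estimates with 95% confidence intervals.*

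State also whether these tests are run within each arm. If the sponsor wants to keep a formal pre- versus post-surgery test, apply Holm to the three fixed contrasts. It never rejects fewer hypotheses than Bonferroni, and power per baseline contrast is about 62-65% against 60%.

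The cost is a wording change in two places, with no new patients, samples or assays. Under the two-contrast family, the pre- versus post-surgery and later contrasts lose their formal significance tests.
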